13.4 Publication Policy

The sponsor believes that results of applicable clinical studies should be published in peer-reviewed literature in a timely, accurate, complete and balanced manner, regardless of study outcomes, whenever possible. As such, at the conclusion of this study, an article may be prepared for publication in a reputable scientific journal. Formal presentation(s) or publication(s) of data collected from this study will be considered as a joint publication

by the investigator(s) and the appropriate personnel of the Sponsor. Authorship will be based on generally accepted criteria of the ICMJE (International Committee of Medical Journal Editors) and determined by mutual agreement.

The publication of the principal results from any single-center experience within the study is not allowed until the preparation and publication of the multicenter results. Exceptions to this rule require the prior approval of the Sponsor. The analysis of other pre-specified and non-pre-specified endpoints will be performed by the Sponsor or its designee. Such analyses, as well as other proposed investigations or manuscripts will require the approval of the Sponsor.

13.5 Study Registration

In compliance with Title VIII of Public Law 110-85, known as FDA Amendments Act of 2007 (FDAAA), the Sponsor will register this study studies and disclose study results in a publicly accessible database (i.e., ClinicalTrials.gov). This study will be registered no later than 21 days after commencing enrollment. Study results will be posted to the website within 12 months of the last participant visit.

13.6 Termination of Study

The Sponsor reserves the right to suspend enrollment or terminate the study at any time for any reason. The Sponsor may suspend enrollment or terminate the study at a specific investigational site for reasons including, but not limited to, inadequate data collection, low participant enrollment rate, achievement of the total enrollment, conditions imposed by the reviewing IRB/EC and/or non-compliance with this protocol or other clinical research requirements. Written notice will be submitted to the Investigator in advance of such termination.

In the event of study suspension or termination, the Sponsor will send a report outlining the circumstances to the IRB/EC, and all Investigators and Regulatory Authorities as required by regulation.

14 ETHICAL AND REGULATORY CONSIDERATIONS

14.1 IRB/EC Approval

Investigators or designees must submit the study protocol, Informed Consent Form (if applicable), and all other locally required documentation to an appropriate IRB/EC and obtain study-specific written approval (favorable opinion) before being allowed to participate in the study. Before commencement of the study, the Investigator or designee must provide the Sponsor with written documentation of such approval. The IRB/EC must give written renewal of the original approval at least annually to continue the study. A copy of the written renewal must be provided to the Sponsor.

The IRB/EC will be notified of any amendments to the protocol, as well as possible associated information and consent form changes, where applicable, and written approval (favorable opinion) will be obtained prior to implementation, as applicable.

The Investigator or designee is responsible for fulfilling any conditions of approval imposed by the IRB/EC, such as regular safety reporting, study timing, etc. The Investigator or designee will provide the Sponsor with copies of such reports.

14.2 Informed Consent and Confidentiality

Prior to any study procedure, the Investigator (or designee) must explain to each participant in layman's terms, the nature of the study, its purpose, expected duration, and the risks and benefits of study participation. Also, participant will be informed of uses and disclosures of their medical information for research purposes, and their rights to access information about them. All applicable national privacy laws (e.g., HIPAA requirements in the U.S.) will be followed in this study. The participants must be informed of their right to withdraw from the study at any time and for any reason without sanction, penalty, or loss of benefits to which they are otherwise entitled, and that withdrawal from the study will not jeopardize their future medical care. Participants will be informed of their right to new information and/or findings relating to the clinical study, and the process by which this information is made available. After this explanation, given sufficient time to decide whether to participate, before any study procedure is conducted, and before entering the study, the participant must voluntarily provide consent in accordance with 21 CFR Parts 50 and 56 and ISO 14155:2020(E). The participant will receive a copy of his/her signed ICF.

14.2.1 Confidentiality

Participant confidentiality must be strictly held in trust by the Investigator, study staff, and the Sponsor. Participant confidentiality and anonymity will be

maintained by removal of identifiers from any data, documentation, or clinical samples submitted to the Sponsor.

Any data collected meeting the definition of protected/confidential health information or personal identifying information will be collected and maintained using the designated authorizations and following privacy procedures as specified in the applicable health authority regulations.

The Sponsor-Monitor, authorized representatives of the sponsor, and/or applicable Health Authorities may inspect all documents and records required to be maintained by the Investigator. The Investigator/Site will permit access to such records.

14.3 Regulatory Status

The PureWick™ Male External Catheter is a Class I, 510(k) exempt device currently marketed in the United States and will be evaluated for its approved indication. The comparator device, Sage PrimoFit™, is also a commercially available device which is Class I, 510(K) exempt. Institutional Review Board (IRB) submission of this study plan along with IRB study approval or waiver is required.

14.4 Statement of Compliance

This clinical investigation will be conducted in compliance with the protocol and following regulatory requirements:

- 21 CFR 50, 54, 56 and 812;
- 21 CFR 812.28(a)(1) (Good Clinical Practice);
- ISO14155:2020 (Good Clinical Practice);
- Ethical principles of the Declaration of Helsinki, in its current revision; and
- Applicable sections of the national laws and regulations.

The clinical investigation will not commence at a clinical site until approval (favorable opinion) from the respective IRB/EC has been received. All additional requirements imposed by the IRB/EC(s) will be followed. Involvement of the national competent authorities (e.g., by notification, seeking authorization) will be accomplished as required by national laws and regulations.

16 APPENDICES

16.1 Appendix 1: PureWick™ Male External Catheter Instructions for Use (IFU)

Instructions for Use

PUREWICK™

MALE EXTERNAL CATHETER

Male External Catheter Kit

Contents:

- 1 PureWick™ Male External Catheter
- 1 Pack Peri-Care Wipes
- 1 Drying Wipe

Setup:

1. Connect a canister to wall suction and set to a minimum of 40mmHg continuous suction. Always use the minimum amount of suction necessary.
2. Using standard suction tubing, connect the device to a collection canister.
Note: Collection canister and suction tubing are not included. If hospital policy allows and if using a graduated canister, captured urine may be used for approximate urine output measurement.

Peri-care and Placement:

[figure not shown]
[figure not shown]
3. If there is significant pubic hair, trim or clip the pubic hair. Perform perineal care using the included wipes and assess skin integrity. Follow and document per hospital protocol.
Note: Use the included drying wipe to ensure skin is dry prior to placement of the device. Moisture on skin will weaken the adhesive.
4. Orient the device, aligning drainage fitting towards the feet of the patient. Slide the opening of the device over the penis until close to the pelvic skin. Center penis within the opening. Remove adhesive liner and press the device against the pelvic skin to adhere. Ensure base has fully adhered around the base of the penis.
Note: The scrotum should not be placed inside the device.

Removal:

5. To remove the device, gently lift the top edge of the device off the skin. In a slow, downward peeling motion, remove the device. If necessary, use a warm wet compress (such as a wet washcloth) to help loosen adhesive.
Warning: To avoid potential skin injury, never pull the device directly away from the patient. Always peel in the direction from head to foot.

Maintenance:

6. Replace the device at least every 24 hours or if soiled with feces, blood, or semen.

BAIRD

Protocol Number: UCC-23AC022

CONFIDENTIAL

Version:1.0

Date: 16May2023

PUREWICK™

MALE EXTERNAL CATHETER

Indication for use:

The device is intended for non-invasive urine output management in male patients.

Contraindications:

- Patients with urinary retention

Warnings:

- Do not use on irritated or compromised skin.
- Do not cover fresh surgical wounds with the device.
- Do not use the device with any material or in any position that does not allow for sufficient airflow.
- To avoid potential skin injury, never pull the device directly away from the patient. Always peel in the direction from head to foot.
- Discontinue use if an allergic reaction occurs.
- After use, this product may be a potential biohazard. Dispose of in accordance with applicable local, state, and federal laws and regulations.

Precautions:

- Not recommended for patients who are:
 - Agitated, combative, or uncooperative and might remove the device.
 - Having frequent episodes of bowel incontinence without a fecal management system in place.
 - Experiencing skin irritation or breakdown at the site.
- Do not use barrier cream on the penis or pubic skin around the base of the penis when using the device. Creams may impede suction or weaken adhesive.
- Proceed with caution in patients who have undergone recent surgery of the external urogenital tract, penis, or pubic area.
- Always assess skin for compromise and perform perineal care prior to placement of a new device.

Recommendations:

- Perform each step with clean technique.
- Prior to connecting the device to hospital wall suction tubing, verify suction function by covering the open end of the suction tubing with one hand and observing the pressure dial. If the pressure does not increase when the line is covered, verify that the tubing is secured, connected, and not kinked.
- Ensure the device remains connected after turning the patient, monitoring for pulling and tension on the device. Remove the device prior to ambulation.
- Assess device placement and patient's skin at least every 2 hours.
- Change suction tubing per hospital protocol or at least every thirty (30) days.

 Units	EXTERNAL USE ONLY
 Single Use	 Non-sterile
 Catalog Number	 Do not use if package is damaged
 Lot Number	 Use By date

 Not Made with
Natural Rubber Latex

BARD

16.2 Appendix 2: Sage PrimoFit™ Instructions for Use (IFU)

Sage

PrimoFit™

External Urine Management
for the Male Anatomy

stryker

Male
[anatomy]

Contents: (1) PrimoFit, adult size **Reorder #5404**

- Single use only.
- Not made with natural rubber latex.
- Non-sterile.

Indications

For the non-invasive external collection of urine for adult patients with male anatomy who require urine management.

Contraindications

- Do not use on patients with urinary retention.

Cautions

- Not intended for use on patients in the prone position.
- Not intended for use on patients with female anatomy.
- Not intended for use for stool collection.
- Use caution if using on patients with altered mental status.

Supplies needed

- Suction canister
- Suction tubing

Directions

Prior to use

- Perform skin assessment every 2 hours per hospital protocol.
- Refer to manufacturer's instructions for suction set up.
- Ensure patient meets hospital protocol prior to placing device. If necessary, clip patient hair per hospital protocol.

Placement

- Step 1** Set up suction canister and tubing according to hospital protocol. Replace tubing and empty and/or replace suction canister per hospital protocol.
- Step 2** Place patient in supine position and separate patient's legs.
- Step 3** Clean, prep and dry patient's genital area according to hospital protocol. If necessary, clip patient hair per hospital protocol.
- Step 4** Remove device from packaging.
- Step 5** Remove the base adhesive liner. (Figure 1)
- Step 6** Position the device with adhesive side toward the patient, with the tabs facing upward and the opening of the base adhesive in line with the patient's penis.
- Step 7** Holding the tabs, position the base adhesive up and around the patient's penis against the skin. To ensure adequate adhesion, apply pressure all the way around the base adhesive against the skin. (Figure 2)
- Step 8** Position the patient's penis into the chamber. (Figure 3)
- Step 9** Remove the adhesive pad liner (Figure 4). Pull the device up until fully extended over the patient's penis and suprapubic region and adhere the adhesive pad onto the patient's abdomen. (Figure 5)
- Step 10** Ensure adequate length of suction tubing is available. Attach suction tubing to the device at the suction tubing adapter. Ensure connection of suction tubing to device is secure and connected at all times while device is in use. Confirm there are no kinks in the tubing and that tubing does not run under the patient. (Figure 6)
 - Secure tubing per hospital protocol.
- Step 11** Set vacuum to low, continuous suction at a minimum of 60mmHG. Always use the minimum amount of suction necessary.
- Step 12** Return patient's legs to a closed position.
 - Assess device periodically to ensure proper placement, particularly after turning or repositioning patient.
 - Device can be left in place for up to 24 hours. Replace device if soiled with stool or bodily fluids other than urine. Discard device according to hospital protocol and local regulations.

Removal

- Step 1** Place the patient in the supine position and separate patient's legs.
- Step 2** Gently remove the adhesive pad from the patient's abdomen.
- Step 3** Remove the patient's penis from the chamber.
- Step 4** Gently remove the base adhesive by pulling the tabs down and away from the patient's penis.
- Step 5** Assess skin integrity and perform perineal care.
- Step 6** Disconnect device from suction tubing and discard device according to hospital protocol and local regulations.

Discontinue use

- When independent or assisted toileting is feasible.
- During patient ambulation.

Product part identification:

[figure not shown]

Figure 1

[figure not shown]

Figure 2

[figure not shown]

Figure 3

[figure not shown]

Figure 4

[figure not shown]

Figure 5

[figure not shown]
[figure not shown]

Figure 6

Manufactured for: Sage Products LLC
 [name] • [name]
 [name] • stryker.com
 Assembled in U.S.A.
 U.S. Patents: stryker.com/patents

For a French-Canadian translated version of the instructions for use contact Stryker Customer Service at [name]. In Canada, this product is not intended to be sold to the general public.

R48050

6 18029 60044 8

16.3 Appendix 3: Participant Comfort Scale Survey

To be completed by each participant once per device (total of 2 per participant).

Participant Number:		Void # (Void 1 or Void 2)		
Now that you have experienced the use of the device as well as voiding with the device in place, please answer the following questions considering the use of the current male external catheter.				
1. On a scale of 1 to 5 where 1 is very uncomfortable and 5 is very comfortable, how comfortable was the placement of the male external catheter?				
1 Very uncomfortable	2 Uncomfortable	3 Neither comfortable nor uncomfortable	4 Comfortable	5 Very Comfortable
2. On a scale of 1 to 5 where 1 is very uncomfortable and 5 is very comfortable, how comfortable was the device while you were voiding ?				
1 Very uncomfortable	2 Uncomfortable	3 Neither comfortable nor uncomfortable	4 Comfortable	5 Very Comfortable
3. On a scale of 1 to 5 where 1 is very uncomfortable and 5 is very comfortable, how comfortable was the removal of the male external catheter?				
1 Very uncomfortable	2 Uncomfortable	3 Neither comfortable nor uncomfortable	4 Comfortable	5 Very Comfortable
4. On a scale of 1 to 5 where 1 is very unlikely and 5 is very likely, how likely would you be to recommend the male external catheter to one of your loved ones?				
1 Very Unlikely	2 Unlikely	3 Neither Likely nor Unlikely	4 Likely	5 Very Likely

Protocol Number: UCC-23AC022

CONFIDENTIAL

Version:1.0

Date: 16May2023

16.4 Appendix 4: Professional Ease of Use Questionnaire

To be completed by HCP after each participant void.

HCP:		Void #:		
Now that you have experienced the application and removal of the device for this participant, please answer the following questions using your professional opinion in regard to device ease of use for this specific participant.				
On a scale of 1 to 5 where 1 is very difficult and 5 is very easy, how easy was the placement of the device?				
1 Very difficult	2 Somewhat difficult	3 Average difficulty	4 Somewhat easy	5 Very easy
On a scale of 1 to 5 where 1 is very difficult and 5 is very easy, how easy was the removal of the device?				
1 Very difficult	2 Somewhat difficult	3 Average difficulty	4 Somewhat easy	5 Very easy

# 1 Introduction

## 1.1 Background and Rationale

The purpose of this study is to provide clinical evidence to compare the effectiveness and comfort of PureWick™ Male against a comparator for non-invasive urine output management in patients with varying male anatomy.

## 1.2 Objectives

### 1.2.1 Primary Objectives

To assess the performance of the PureWick™ Male (System) against an established comparator (Stryker/ Sage PrimoFit™).

### 1.2.2 Secondary Objectives

- To assess the performance of the PureWick™ Male (System) in patients that are unable to use traditional sheath style condom catheters.
- To assess participant comfort after using the MEC.
- To assess ease of use by HCP in placing the MEC.

# 2 Study Description

## 2.1 Study Design

This is a Prospective, Randomized, Crossover, Single-blind, Single Center Healthy Volunteer Study conducted over 1 day, with 2 voids using the PW Male external catheter vs. comparator Sage PrimoFit™. This study is designed to assess the performance, comfort, and ease of use of the PW Male external catheter as compared to the comparator product

## 2.2 Study Population

Adult male healthy volunteers with a target of 50% of subjects in each of the following cohorts:

- Cohort A: Non morbidly obese men: BMI <40
- Cohort B: Morbidly Obese men: BMI ≥40

Inclusion Criteria:

- Adult Male Patients ≥18 years old
- Male anatomy at time of enrollment
- Ability to speak and understand English
- Willing to comply with all study procedures in the protocol
- Able to independently void urine
- Provision of signed and dated informed consent form

Exclusion Criteria:

- Urinary incontinence which does not allow the subject to spontaneously void
- Frequent episodes of bowel incontinence
- Has Urinary Retention
- Has any irritation, wound, open lesion, at the application site, on the genitalia, perineum, or sacrum
- Recent surgery of the external urogenital tract, penis, or pubic area
- Not able to comply with study procedures independently without required assistance
- Any other condition that, in the opinion of the investigator, would preclude them from participating in the study

## 2.3 Randomization and Blinding

Subjects will be randomized using a block size of 4 and using a 1:1 ratio to one of the two treatment sequences. Subjects randomized to Sequence 1 will use PureWick MEC first, followed by Sage PrimoFit. Subjects randomized to Sequence 2 will use Sage PrimoFit first, followed by PureWick MEC. Randomization will be stratified by cohort. Cohort A consists of non-morbidly obese subjects (BMI < 40). Cohort B consists of morbidly obese subjects (BMI ≥ 40). The randomization schedule is created using R (R Core Team, 2021). Randomization seed is specified in the R script.

The investigational site will receive a set of randomization envelopes for each cohort that are numbered in sequential order. Within each randomization envelope, a treatment sequence assignment card will be enclosed, containing the sequence number and device to be used for each void. The randomization envelopes are to be opened in sequential order (as noted on the envelope) and are to be opened only when all inclusion/exclusion criteria are met.

The Investigator and Sponsor will know which device the participant is being treated with at any given time. Participants will remain blinded to treatment order until the study is complete.

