------------------------------	--

Protocol Title	Evaluating the efficacy and comfort of the PureWick™ male external catheter against a comparator in Healthy Volunteers
	
The participant will be asked to complete a brief survey to assess device comfort immediately after the completed void.
 
The HCP will be asked to complete a brief survey to assess device ease of use for the participant just treated.
 
Void 2:
 
Participants will be asked to not void and to drink approximately 16 fluid ounces of liquid. When the participant feels the need to void (a second time), the HCP will confirm via bladder scanning procedure that the bladder volume is $\geq 125\text{mL}$. If the volume is determined to be inadequate, the participant will be asked if they can wait to void, drink additional fluids as tolerated and be re-assessed in approximately 30 minutes. If the participant does not feel comfortable waiting to void, they will be allowed to proceed with void 2.
 
Void 2 will be repeated per the Void 1 procedure using the 2nd device assigned per randomization.
 
The participant will complete a brief survey (for the second device sequence) immediately following the void to assess device comfort and will then be discharged from the study.
 
The HCP will complete a brief survey to assess device ease of use for the participant just treated.

Investigational Sites	1 site in the US
Data Monitoring Committee	Not Applicable
Regulatory Status	
Post-Market
 
The investigation will use both the PureWick™ Male External Catheter and Sage PrimoFit™ for its intended purpose.

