5 STUDY POPULATION

Adult male healthy volunteers will be recruited for this study with a target of 50% of participants in each of the two BMI cohorts. Participants will be recruited from an existing pool of volunteers in a database owned by a third-party research vendor. Basic screening questions will be used to identify potential participants and full screening against inclusion/exclusion criteria will be completed on the day of enrollment.

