5.2 Exclusion Criteria

Participants are excluded from the study if any of the following criteria apply:

1. Urinary incontinence which does not allow the subject to spontaneously void
2. Frequent episodes of bowel incontinence
3. Has Urinary Retention
4. Has any irritation, wound, open lesion, at the application site, on the genitalia, perineum, or sacrum
5. Recent surgery of the external urogenital tract, penis, or pubic area
6. Not able to comply with study procedures independently without required assistance
7. Any other condition that, in the opinion of the investigator, would preclude them from participating in the study

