6.5.1 Randomization

Participants will be randomized 1:1 to one of the two treatment sequences. Subjects randomized to Sequence 1 will use PureWick™ MEC first, followed by

Sage PrimoFit™. Subjects randomized to Sequence 2 will use Sage PrimoFit™ first, followed by PureWick™ MEC. Randomization will be stratified by cohorts (non-morbidly obese men: BMI <40 or morbidly obese men: BMI ≥40). This design allows for the evaluation of elements such as carryover effect, period effect, and sequence effect.

The study site will receive randomization envelopes for each cohort that are numbered in sequential order. Within each randomization envelope, a treatment sequence assignment card will be enclosed. The randomization envelopes should be opened in sequential order only when all eligibility criteria are met.

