6.5.2 Blinding/Masking

Complete study blinding is not feasible due to possible HCP familiarity with the study devices and visual differences between the product packaging. As such, this is a single-blind study in which only participants are blinded to which device is which. The Investigator and Sponsor will know which device the participant is being treated with at any given time.

Blinding procedures will be reviewed at the time of site initiation by a Sponsor representative. During review of the study and the informed consent process with participants, blinding and rationale should be discussed with the participant.

Any communication to the study personnel placing the device as to the randomized treatment sequence should be done in a way as to prevent the participant from overhearing. Devices should be referred to throughout the study period as 'Device A' and 'Device B' rather than the marketed product name.

Participants will remain blinded to treatment order until the study is complete.

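### A fixed block size of 4 at a single unblinded site lets anyone who knows or works out the block size foresee about a third of sequence assignments, which weakens allocation concealment; the risk to the primary comparison is minor and conditional

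*SAP*

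**What the plan says.** SAP 2.3 sets a single block size: "Subjects will be randomized using a block size of 4 and using a 1:1 ratio to one of the two treatment sequences". It adds: "Randomization will be stratified by cohort". SAP 2.2 describes the intake as "Adult male healthy volunteers with a target of 50% of subjects in each of the following cohorts", so with about 50 men enrolled each list holds about 25.

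The Protocol synopsis gives "1 site in the US". Protocol 6.5.1 says: "The study site will receive randomization envelopes for each cohort that are numbered in sequential order". Envelopes are to be opened in order and only once eligibility is met (Protocol 6.5.1 and 7.4, SAP 2.3). On blinding, Protocol 6.5.2 says: "The Investigator and Sponsor will know which device the participant is being treated with at any given time".

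The block size is in the SAP but not in the Protocol's randomization sections (6.5.1 and 7.4). Neither document says whether site staff see the SAP, whether envelopes are sealed and opaque, or who holds and opens them.

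What is randomized is device order. Under Protocol 6.5 each man is his own control, and the primary test is a two-sided paired t-test (Protocol 10.5, SAP 5.2.2).

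**The concern.** When past assignments are visible and the block size is constant, the tail of each block can be read off before the envelope is opened. Opening envelopes in order after eligibility does not prevent this, because the prediction comes from cards already used. Even someone not told the block size could notice that each list returns to balance after every fourth man.

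A prediction matters only if it can be acted on. One possible route is the exclusion worded "Any other condition that, in the opinion of the investigator, would preclude them from participating in the study", which leaves room for judgement. Another might be the order in which volunteers are called in.

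At stake is the protection that randomized order gives the paired comparison. The two voids are not made under the same conditions: men arrive with a full bladder for Void 1, while Void 2 follows about 16 ounces of fluid and a bladder scan. The primary test has no period or sequence term. These appear only in an exploratory regression, where they are optional.

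**Working it through.** **The plan's own figure.** A paired t-test with n = 44, two-sided alpha 0.05 and a mean difference of 0.5 SD has noncentrality 0.5 × √44 on 43 df. Power is 0.9000, so the stated 90% reproduces. The documents give no figure for predictability.

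**Certain assignments.** A 1:1 block of 4 has six equally likely orders.
- AABB and BBAA fix positions 3 and 4: two certain assignments each.
- ABAB, ABBA, BAAB and BABA fix position 4 only: one each.
- Expected per block: (2 × 2 + 4 × 1)/6 = 1.333 of 4 = 33.3%.
- Two cohorts of 25 (six full blocks plus one man): 2 × 6 × 1.333 = 16.0 of 50 = 32.0%.
- Two cohorts of 22 (five full blocks plus two men): 2 × 5 × 1.333 = 13.3 of 44 = 30.3%.
- Best-guess accuracy per block: (0.5 + 0.667 + 0.667 + 1)/4 = 70.8%. In a cohort of 25 it is 70.0%.

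Stratification does not raise these shares; it means that two tallies must be kept. If staff had to infer the pattern and did so only after three blocks (an assumption), 3 × 1.333 = 4 of 25 assignments would be certain, or 16%.

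**Other schemes, cohorts of 25.** The mixed-block rows are simulated, with a guesser who knows the set of sizes but not the block boundaries.

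| Scheme | Certain | Best guess right |
|---|---|---|
| Fixed 4 | 32.0% | 70.0% |
| Mixed 4/6 | about 6% | about 68% |
| Mixed 4/6/8 | about 2% | about 67% |

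**When the primary test is affected.** Let τ be the device effect and δ a man's Void 1 minus Void 2 effect. His paired difference (PureWick minus PrimoFit) is τ + δ if PureWick comes first and τ − δ if it comes second. With equal sequence sizes the mean is τ + (p1 − p2)/2, where p1 and p2 are the mean δ in the two sequences.
- A man's general level of capture drops out.
- A δ common to all men gives p1 = p2 and cancels.
- Bias arises only if δ differs between men and the sequences receive different kinds of men.

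**Illustrative size.** Assume two kinds of men whose δ differs by D points. A share s of slots is steered in PureWick's favour, and the other slots have the same mix in both sequences. Then p1 − p2 = sD and the bias is sD/2. Take the plan's example SD of 10 and n = 44. The chance of a false PureWick win is the upper tail of a noncentral t (43 df, noncentrality bias × √44/10) beyond 2.017. D and s are assumptions with no source in the documents.

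| Steered | D = 2.5 | D = 5 | D = 10 |
|---|---|---|---|
| None | 2.5% | 2.5% | 2.5% |
| A quarter of certain slots (s = 0.083) | 2.9% | 3.4% | 4.6% |
| All certain slots, s = 0.303 | 4.3% | 7.1% | 16.4% |
| All certain slots, s = 0.333 | 4.6% | 7.8% | 19.0% |

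The bias in the last row is 0.4, 0.8 and 1.7 points. A simulation with 22 men per cohort that adds the between-man spread in δ to the SD of 10 gives lower rates: 4.4%, 6.2% and 13.3%.

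**The case against.** The strongest reply is that the design already limits the damage. Only device order can be predicted, and each man supplies his own control. A full bladder at Void 1 against a refilled one at Void 2 describes an effect shared by all men, which cancels. To bias the result, staff would need a trait that marks out men with a different δ and is recognisable before the envelope is opened. The documents name none. BMI category, the obvious visible candidate, is the stratification factor, and the assessment of genital anatomy follows randomization in Protocol 7.5. This stands, and it is why the point is minor.

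Steering is also awkward. Men attend one scheduled visit, screen failures may not re-screen (Protocol 5.4), and reasons for failure are logged (Protocol 7). As to choosing whom to call in, Protocol 5 says "Participants will be recruited from an existing pool of volunteers in a database owned by a third-party research vendor", and nothing shows that site staff control the order. This largely stands, though the investigator-opinion exclusion remains.

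A reader might infer that allocation is not concealed at all. The documents do not support that: numbered envelopes opened in order after eligibility give partial concealment, knowledge of the block size at the site is not established, and the person who opens the envelopes is not named.

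Finally, varying the block size does little against someone who acts on best guesses. Bias would then be (2 × accuracy − 1) × D/2, or 0.20D now and 0.168D at 66.8% accuracy. At D = 10 the false-win rate after the change would be about 19%. This stands: the change removes certainty, not all predictability.

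**Conclusion.** A fixed block of 4 within each cohort, at one site with unblinded staff, makes about a third of sequence assignments certain to anyone who knows or infers the block size and tracks each envelope set: 33.3% per full block, 30% to 32% at the planned sizes. Concealment is weakened, not absent.

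For the primary test the risk is minor and conditional. Bias is zero without steering, and zero if the Void 1 versus Void 2 effect is the same for all men and the sequences are balanced. A reader might take the 19% false-win rate as an expected error rate. It is a hypothetical upper illustration for certainty-based steering: it needs a gap D equal to the plan's full example SD and every certain slot steered, and the documents support neither. The case for change is that standard protection costs almost nothing, not that the planned result is unsound. Priority is minor.

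**What to change.** In SAP 2.3, replace the single block size of 4 with permuted blocks of randomly varying size (for example 4, 6 and 8) within each cohort. State that block sizes and schedule are not disclosed to site staff before database lock, and hold them in a restricted file kept by someone who neither enrols men nor places devices. It would also help to state that envelopes are sealed and opaque, and who holds them. If enrolment has begun, apply the new scheme to unopened envelopes.

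The cost is one line in the R script, a sentence or two in the SAP and a reprinted envelope set, with no extra participants or visits. The downside is that the largest possible sequence imbalance per cohort rises from 2 to 4 men (half of the largest block), with negligible loss of precision.
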